### 11.2 Safety Data Handling

Adverse event toxicity grade will be classified using NCI-CTCAE Version 4.03 criteria (Grade 1 – Grade 5). If a subject has multiple occurrences of the same system organ class (SOC) or

preferred term, then only the most severe event will be summarized in the tables for that SOC and preferred term. Adverse events of  $\geq$ Grade 3 will also be summarized. A missing toxicity grade will not be imputed.

The AE analysis will be repeated for SAEs and AEs leading to dose reduction or discontinuation.

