**If an AESI also meets SAE criteria, the event will be reported as an SAE per Section 7.1.6.**

**AESIs observed with durvalumab and tremelimumab and those considered AESIs for the purpose of this study are listed below.** Further information on these AESIs (e.g. presenting symptoms) can be found in the current versions of the durvalumab (MEDI4736) and tremelimumab Investigator's Brochures. Guidelines for the management of subjects experiencing toxicities for durvalumab and tremelimumab can be found in Section 8.3 and in the following Medimmune guideline: ***“Medimmune’s Dosing Modification and Toxicity Management Guidelines for Immune-mediated, Infusion Related, and Non Immune-mediated Reactions (MEDI4736 (durvalumab) Monotherapy or Combination therapy with Tremelimumab or Tremelimumab monotherapy).”***

- **Diarrhea/Colitis and intestinal perforation**  
Diarrhea and colitis are the most commonly observed treatment-emergent AEs following dosing with study medications. In rare cases, colon perforation may occur that requires surgery (colectomy) or can lead to a fatal outcome, if not properly managed.
- **Pneumonitis/Interstitial lung disease (ILD)**  
Adverse events of pneumonitis have been observed with anti-PD-1, and anti-PD-L1 antibodies (see IB). Initial work-up should include high-resolution CT scan, ruling out infection, and pulse oximetry. Typically, pulmonary consultation is required.
- **Hepatic Function Abnormality (Hepatitis / transaminase increases)**  

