#### 8.3.1 Durvalumab and Tremelimumab Dose Modification Due to Toxicity

Durvalumab (MEDI4736) and tremelimumab administration may be modified or discontinued as a result of toxicities as described in the table below.

Additional information and guidance regarding dose modification due to toxicity are provided from Medimmune in the following guidelines:

***“Medimmune’s Dosing Modification and Toxicity Management Guidelines for Immune-mediated, Infusion Related, and Non Immune-mediated Reactions (MEDI4736 (durvalumab) Monotherapy or Combination therapy with Tremelimumab or Tremelimumab monotherapy).”***

Dose modifications will not be required for AEs that are clearly not attributed to durvalumab or tremelimumab (such as an accident) or for laboratory abnormalities that are not deemed to be clinically significant.

MEDI4736 (M) and Tremelimumab (T) Dose Modification Due to Toxicity
Note: If M and T dosing is held temporarily until resolution of the event as per instructions below, treatment should resume at the next scheduled treatment date.
Immune-related Adverse Events (irAEs) Immune-related adverse events are defined as AEs of immune nature (i.e., inflammatory) in the absence of a clear alternative etiology. Maximum supportive care, including immunosuppressive medications, such as high dose steroids, is allowed to induce resolution of the event. However, infliximab should not be used for management of immune-related hepatitis. In addition to the criteria for permanent discontinuation of M and T depicted below, permanently discontinue M and T also for: 

• Any Grade rash with bullous skin formations.

• Inability to reduce corticosteroid to a dose of <math>\leq 10</math> mg of prednisone per day (or equivalent) within 12 weeks after last dose of study drug/regimen.

• Recurrence of a previously experienced Grade 3 treatment-related AE following resumption of dosing.

• Any Grade biopsy-proven immune-mediated myocarditis.

 Grade 1 

• In general, no dose modification required.

• For pneumonitis/interstitial lung disease and myocarditis, consider holding M and T dosing as clinically appropriate and during diagnostic work-up for other etiologies.

CONFIDENTIAL

## Grade 2

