- For *pneumonitis/interstitial lung disease, myocarditis, and elevated serum creatinine (e.g., nephritis or renal dysfunction)*, always discontinue M and T permanently.
- For *asymptomatic increases of amylase or lipase* levels, hold M and T, and if complete work up shows no evidence of pancreatitis, M and T may be continued.
- For *hepatitis*, discontinue M and T permanently for (1) transaminases or bilirubin not resolving to  $\leq$  Grade 1 or baseline within 14 days, (2) transaminases  $> 8 \times$  the upper limit of normal (ULN) or bilirubin  $> 5 \times$  ULN, or (3) any case meeting Hy's law criteria (as defined in FDA Guidance Document "Drug-Induced Liver Injury").
- For *rash*, M and T should be held until resolution to  $\leq$  Grade 1 or baseline.

CONFIDENTIAL

MEDI4736 (M) and Tremelimumab (T) Dose Modification Due to Toxicity

Grade 4
 
 
• In general, discontinue M and T permanently.
 
• For endocrinopathies, follow Grade 2 instructions above.
 
• For asymptomatic increases of amylase or lipase levels, hold M and T, and if complete work up shows no evidence of pancreatitis, M and T may be continued.
 

Infusion-related Reactions
 
Grade 1
 
 
• The infusion rate of M and T may be decreased 50% or temporarily interrupted until resolution of the event.
 
• Acetaminophen and/or antihistamines may be administered per institutional standards at the discretion of the Investigator.
 
• Premedication for subsequent doses should be considered.
 
• Steroids should not be used for routine premedication of <math>\leq</math>Grade 2 infusion reactions
 
 
Grade 2:
 
 
• Same as Grade 1, but consider giving subsequent infusions at 50% of the initial infusion rate.
 
 
Grade 3 and 4:
 
 
• The infusion must be stopped immediately and treatment permanently discontinued.
 
• Manage severe infusion-related reactions per institutional standards (e.g., IM epinephrine, followed by IV diphenhydramine and ranitidine, and IV glucocorticoid).
 

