## 8.4 BI 1361849 Toxicity Management and Dose Modification

If a toxicity occurs that requires toxicity management in accordance with Sections 8.3 or 8.4, and the toxicity causing drug can be clearly identified, then the respective guideline should be followed. If the toxicity causing drug cannot be identified, then the more conservative guideline should be followed.

In case of adverse events considered related to BI 1361849 or to the combination of BI 1361849 with durvalumab or with durvalumab and tremelimumab, treatment with the vaccine (or with the vaccine as well as durvalumab and/or tremelimumab) may have to be withheld. If a subject experiences any  $\geq$  CTCAE Grade 3 treatment-related AE not fulfilling the criteria for permanent discontinuation, study drug treatment may be resumed after the toxicity has returned to baseline or Grade  $\leq$  1 within a time period  $\leq$  4 weeks for vaccination. No dose reduction of the vaccine dose is foreseen.

Administration of BI 1361849 must be withheld in the following cases and may be postponed to later time points within the allowance windows defined in the table below:

- Subject has fever  $\geq$  38.5 °C or other signs of an acute systemic infection on the day of administration.
- Subject has a suspected autoimmune disease - in this case BI 1361849 should be omitted until the diagnosis is confirmed or excluded. In case of a confirmed autoimmune disease the Sponsor should be contacted to decide whether BI 1361849 should be permanently discontinued.
- Subject has ongoing BI 1361849 related systemic toxicity of initially CTCAE grade 3 or higher that has not yet resolved to at least grade 1 or baseline.
- Subject has a suspected pneumonitis or other interstitial lung disease (ILD). In this case BI 1361849 should be omitted until the diagnosis is confirmed or excluded. In case of confirmed pneumonitis or other ILD, BI 1361849 should be discontinued.
- Subject has an important medical event that in the investigators opinion might be worsened by the administration of BI 1361849 (e.g. acute cardiac events that may deteriorate in case of fever induced by BI 1361849).

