Vaccinations should always be administered within the planned time windows given in Section 3.2. However, vaccinations may have to be delayed to allow for recovery of AEs prior to continuation of vaccine treatment. For these circumstances, maximal allowance windows have been specified below. After the delayed vaccination all subsequent vaccinations must be continued within the schedule relative to the first vaccination presented in the flow chart. If a vaccination cannot be administered within the maximal allowance windows for an administration time point, the vaccine administration for this time point has to be omitted, and further vaccinations should be given at subsequent planned time points according to the flowchart in Section 3.2.

---

CONFIDENTIAL

Maximal allowance windows due to AEs:		
Vaccination	Scheduled Week (Day 1 of)	Total extended visit window from originally scheduled vaccination (days)
2 nd	2	3
3 rd , 4 th , 5 th , 6 th , 7 th	3, 5, 7, 9, 11	7
8 th , 9 th	13, 17	10
10 th and continuing	21, 27 and every 6 weeks	28

In the event that prior to a planned blood sampling time point for immunomonitoring, the immediately preceding vaccination has to be delayed or omitted, the blood sampling has to be delayed in the same fashion to ensure that the blood sample has been obtained within 7 ± 2 days after the immediately preceding vaccination. In the event that the vaccination had to be omitted, blood sampling should occur after the next subsequent vaccine administration.

The following toxicities prohibit continuation of study treatment:

- Grade ≥ 3 study treatment-related anaphylactic reactions.
- Study treatment related AEs that are potentially life threatening or may result in permanent disability.
- Grade ≥ 3 pneumonitis/inflammatory lung disease, or other ILD
- Grade ≥ 3 study treatment-related AEs not recovering to baseline or grade 1 within 4 weeks in case of vaccination. The Sponsor should be contacted in case it is considered justifiable to continue treatment at a later time point, to approve continuation of treatment of BI 1361849, which in any case must not occur before the AE finally has resolved or recovered to baseline or grade 1.

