### 9.1.1 Treatment-Emergent Adverse Events

Treatment-emergent adverse events (TEAEs) are defined as any AEs that started after dosing or worsened in severity after dosing.

An overall AE summary for number of subjects will be presented for the following categories:

- Any Adverse Event
- Any TEAE
- Any Deaths within the AE reporting period
- Any study drug-related adverse event (TRAE) (i.e., related to durvalumab, tremelimumab and/or vaccine)
  - Any durvalumab related TRAE
  - Any tremelimumab related TRAE
  - Any vaccine related TRAE
- Any TEAE  $\geq$  CTCAE Grade 3
- Any TRAE  $\geq$  CTCAE Grade 3
- Any treatment-emergent Serious AEs (SAEs)
- Any Serious TRAEs
- Any TEAE leading to treatment (durvalumab, tremelimumab, and/or vaccine) discontinuation
  - Related to durvalumab
  - Related to tremelimumab
  - Related to vaccine

The following events will be tabulated by SOC and PT. Summaries will be sorted by decreasing frequency of PT within SOC which is sorted alphabetically.

- TEAEs by SOC and PT
- TEAEs by PT frequency only
- Treatment-emergent SAEs
- Treatment-related AEs
  - Durvalumab related
  - Tremelimumab related
  - Vaccine related
- Treatment-related SAEs
- TEAEs leading to treatment (durvalumab, tremelimumab, and/ or vaccine) discontinuation
  - Durvalumab discontinuation
  - Tremelimumab discontinuation
  - Vaccine discontinuation
- DLTs

A summary of TEAEs by SOC, PT and maximum severity, sorted by decreasing frequency of PT within SOC which is sorted alphabetically, will also be provided for:

- TEAEs
- TEAEs  $\geq$  CTCAE Grade 3
- Treatment related AEs
  - Durvalumab related
  - Tremelimumab related
  - Vaccine related
- TRAEs  $\geq$  CTCAE Grade 3

In tabulation by severity grade,

- For a given SOC, only the most severe SOC for each subject will be included.
- For a given PT, only the most severe PT for each subject will be included.

The following listings will be provided:

- All AEs (flag TEAE)

- DLTs
- SAEs
- TEAEs leading to study treatment discontinuation
- TEAEs leading to study drug (durvalumab or tremelimumab) dose modifications
- Deaths in the AE reporting period

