#### **9.1.2 Adverse Events of Special Interest (AESIs)**

AESIs will not be separately presented in this analysis.

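### The SAP analyses AEs leading to dose reduction, an action absent from the protocol's toxicity rules, but has no summary of AE-driven holds, delays or omissions and no grouped view of immune toxicity

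*SAP*

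**What the plan says.** Safety and tolerability is the primary objective in both phases (Protocol 4).

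**Actions analysed.** SAP 11.2, Safety Data Handling: "The AE analysis will be repeated for SAEs and AEs leading to dose reduction or discontinuation". The output list in SAP 9.1.1 has tables for SAEs and for discontinuation of each drug, the vaccine included. It has no table for dose reduction and none for holds, delays or omissions. Its one output on dose changes is a listing: "TEAEs leading to study drug (durvalumab or tremelimumab) dose modifications".

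**Actions the protocol uses.** For the vaccine, Protocol 8.4 states: "No dose reduction of the vaccine dose is foreseen". It requires the vaccine to be withheld for listed events, says that "vaccinations may have to be delayed to allow for recovery of AEs prior to continuation of vaccine treatment", and has a vaccination omitted if it cannot be given within its extended window. For the antibodies, Protocol 8.3.1 states: "Durvalumab (MEDI4736) and tremelimumab administration may be modified or discontinued as a result of toxicities as described in the table below". That table offers holds, permanent discontinuation and, for low-grade infusion reactions, this: "The infusion rate of M and T may be decreased 50% or temporarily interrupted until resolution of the event".

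**Immune toxicity.** Protocol 7.1.8 says the AESIs observed with the two antibodies and "those considered AESIs for the purpose of this study are listed below". SAP 9.1.2 says: "AESIs will not be separately presented in this analysis". The SAP plans no summary of immune-related AEs (irAEs) either.

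**The concern.** The SAP names an action that the toxicity rules do not contain, and has no table for the actions they do contain. A reader of the report who meets an empty dose-reduction category may take it as evidence of good tolerability, although the protocol never offered that action. The interruptions that do show how well the combination is tolerated would go unsummarised, and for the vaccine they would not reach the dose-modification listing.

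Interruptions also bear on the primary dose-evaluation endpoint. Under Protocol 3.1.9, subjects who interrupt treatment for toxicities other than DLTs may in some circumstances be counted as DLT subjects. Under Protocol 4.1.2, a subject without a DLT is evaluable only with at least 4 of the 5 vaccinations in the DLT period. A summary of AE-driven missed vaccinations would let a reader follow those decisions.

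For immune toxicity, the protocol keeps an AESI list, collects irAEs for 90 days after the last dose even if another therapy has started (7.1.5), and asks about them again in Post Study Follow-up (3.1.16). The SAP has no output that draws these events together.

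**Working it through.** **1. Actions against outputs**

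| Action on toxicity | In Protocol 8.3.1 / 8.4? | Summary table in SAP 9.1.1? | In the SAP 9.1.1 dose-change listing? |
|---|---|---|---|
| Lower administered dose | No, for any drug | No (named only in SAP 11.2) | Durvalumab and tremelimumab only, if it occurred |
| Hold, delay or omission: durvalumab, tremelimumab | Yes | No | Yes, if read as a modification |
| Hold, delay or omission: vaccine | Yes | No | No |
| Infusion rate change or interruption | Yes (antibodies) | No | Yes, if read as a modification |
| Discontinuation, per drug | Yes | Yes | Separate discontinuation listing |

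Lower doses do exist elsewhere in the protocol. The 750 mg durvalumab level is a cohort decision (3.1.7.1). Weight-based dosing applies when body weight falls to 30 kg or less (3.1.7.1, Note 2), which could occasionally follow from a weight-loss AE. That is why the category is expected to be empty or nearly so, and not necessarily empty.

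**2. How much dosing lies outside the listing**

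Counted from the dosing table in Protocol 3.1.7, for a subject who completes treatment: vaccine 14 administrations, durvalumab 12, tremelimumab 4.

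- Arm A: 14 / (14 + 12) = 14/26 = 54%.
- Arm B: 14 / (14 + 12 + 4) = 14/30 = 47%.

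The Protocol 3.1.7 table also shows a tremelimumab mark at Cycle 12, which the protocol flowchart and SAP Appendix B do not have. The passages need to be reconciled. If the mark is counted, Arm B is 14/31 = 45%.

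Six vaccine days carry no other drug: Cycle 1 Days 8 and 15, and Day 15 of Cycles 2, 3, 7 and 10.

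**3. Would there be anything to count?**

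The documents give no rate of AE-driven vaccine holds. If a proportion p of subjects has at least one, the chance of seeing one or more such subjects among 20 is 1 − (1 − p)^20.

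- p = 5%: 64.2%
- p = 10%: 87.8%
- p = 20%: 98.8%

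**4. Effect of not grouping immune events**

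The plan's own figure is the exact (Clopper-Pearson) table in Protocol 3.1.6: lower limit = Beta(0.025; x, 21 − x), upper limit = Beta(0.975; x + 1, 20 − x). All 19 rows reproduce to within 0.000005.

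Suppose five immune preferred terms are each reported in one subject of 20 (assumed counts). Each row reads 1/20 = 5% (95% CI 0.1% to 24.9%). Those five rows fit anything from one subject with all five events, 1/20, to five different subjects, 5/20 = 25% (95% CI 8.7% to 49.1%). Only a subject-level any-AESI row tells these apart. A table of AESI categories without that row would still show five rows of 1/20 if the events fell in five categories.

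**5. Do the exposure summaries fill the gap?**

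SAP 8.0 gives duration, number of doses and total dose for each drug. It gives no comparison with scheduled doses and no reason for a missed dose, so a low vaccine count caused by toxicity looks the same as one caused by progression.

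**The case against.** A reader might infer that the main tolerability signals cannot appear in the report. The documents do not support that. SAP 9.1.1 tabulates TEAEs by term and maximum severity, events of Grade 3 or higher, SAEs, DLTs, related AEs per drug and discontinuations per drug, the vaccine included. It also lists every AE.

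A reader might also infer that AESIs are suppressed, or that the dose-reduction result must be 0/20 in each arm. Neither follows. AESI-type events stay in the general tables under their preferred terms, so they are ungrouped and not removed. A fixed 0/20 overlooks weight-based dosing, the general allowance for dosing adjustments in Protocol 3.1.8, and the external toxicity guideline cited in 8.3.1, which is not available here.

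Further points on the other side carry weight. Protocol 4.1.2 does not promise an AESI or dose-hold table, so these are weaknesses of the SAP and not departures from the protocol's analysis section. Protocol 8.3.1 uses dose modification for a scheme made up largely of holds, so the listing can fairly be read to cover antibody holds. Protocol 7.1.5 has the intervention with study drug documented for each AE, so the information exists and may reach the all-AE listing, although the SAP does not say that column will be shown. The table shells are not available. An explicit decision not to group AESIs can be a legitimate reporting choice, though the SAP gives no reason for it.

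What remains is that SAP 11.2 matches neither the protocol's actions nor SAP 9.1.1, no table counts interruptions for any drug, and the vaccine is not named in the one relevant listing.

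**Conclusion.** The point holds within limits. The SAP's rule for AE-driven treatment changes is aimed at an action absent from Protocol 8.3.1 and 8.4, and the actions those sections do use, short of discontinuation, have no summary table. The omission matters most for the vaccine, with about half of scheduled administrations (54% in Arm A, 45% to 47% in Arm B). Grouped immune toxicity is a second, smaller gap: the same ungrouped rows can stand for 1/20 or 5/20 subjects.

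No estimate, sample size or decision rule changes, and the main safety tables are unaffected. It should be corrected because tolerability is the primary objective and the data are already collected.

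The conclusion assumes that the external guideline adds no AE-driven reduction of the administered dose, and that the unseen table shells do not already contain an interruption table. The hold rates and immune-event counts above are illustrations, not predictions.

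**What to change.** **SAP 11.2 and 9.1.1.** Replace dose reduction with dose hold, delay or omission, keeping discontinuation. Tabulate it per arm and separately for durvalumab, tremelimumab and BI 1361849, using the study drug intervention item already recorded for each AE. Add BI 1361849 to the dose-modification listing.

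**SAP 9.1.2.** Replace the sentence with one table per arm of the Protocol 7.1.8 AESI categories, including a subject-level any-AESI row, each shown for any grade, Grade 3 or higher, and leading to discontinuation.

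**Cost.** Two or three extra tables and a prespecified grouping of preferred terms. The grouping needs medical review as well as programming, because the AESI list in Protocol 7.1.8 is open-ended. No new data are needed, and no dose or clinical rule changes. As the SAP is already final, SAP 1.0 requires a later change to the analysis methods to be described in the clinical study report.

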### **11.3 Coding Dictionaries**

Medical history, AEs, and concurrent procedures will be coded using Medical Dictionary for Regulatory Activities (MedDRA V20). Prior and concomitant medications will be coded using the World Health Organization Drug Dictionary (WhoDrugDDEB2\_201703).

### **11.4 Pooling of Centers in Multi-Center Trials**

There will be no pooling of centers.

### **11.5 Multiple Comparisons/Multiplicity**

No adjustments for multiple comparisons or multiplicity will be made.

### **11.6 Examination of Subgroups**

No subgroup analysis will be performed in this study.

### **11.7 Interim Analysis and Data Monitoring**

Interim Safety Reviews will be performed to assess DLTs in the dose evaluation cohorts for determination of RCD. Interim analyses may be performed to analyze the 8- and 24-week endpoints.

## **12.0 QUALITY CONTROL**

All data displays and analyses will adhere to the International Conference on Harmonisation (ICH) Harmonized Tripartite Guideline: Structure and Content of Clinical Study Reports (ICH Topic E3). The clinical monitor will verify that the clinical study is conducted and data are generated, documented (recorded), and reported in compliance with the protocol, GCPs, and any applicable regulatory requirements.

Ludwig Institute for Cancer Research (LICR) or their designee will review all tables, listings, and figures prior to final database lock. Final SAS datasets, programs and outputs will be transferred to LICR at project completion.

### 13.0 TABLES AND LISTING CONVENTIONS

Mock-ups for statistical tables and listings will be provided. Final formats for the statistical tables and listings may deviate from these mock-ups upon agreement with LICR. Footnotes will be used as needed to clarify the information that is presented in the tables and listings. Unless otherwise requested by LICR, the term ‘subject’ will be used in all tables and listings, in accordance with CDISC standards.

The numbering of tables, figures and listings will be in the following order:

Table 14.x.y.z, Figures 15.x.y.z, Listings 16.x.y.z.

The general layout of tables and listings will be as follows:

Ludwig Institute for Cancer Research.

Protocol: LUD2014-012-VAC

Clinical Study Report

Page x of y

Run Date: DDMMYY \_HH:MM

Listing 16.2\_x (or Table 14.x\_x)

<Title>

<Population>

Col 1 Col 2 Col 3 etc.

---

---

---

<Any footnotes>

File Name: <pathname for SAS program>

All tables and listings will use landscape orientation. Margins will be at least 2.0 cm at the top and bottom and at least 0.8 cm on the left and right, excluding headers and footers, in accordance

with electronic Common Technical Document (eCTD) guidelines. Font will be Courier New, unless otherwise specified, with an 8-point font size in most cases. Page numbering will be sequential within each table, listing, and figure. Column headers should be in initial capital letters. Units for numeric data will be included when appropriate.

Tables and data listings will be created from different SAS programs. A single program may produce multiple tables or multiple data listings from the same dataset (e.g., all clinical chemistry data listings may be generated by a single program).

